5. STUDY ENROLLMENT AND WITHDRAWAL

Eligibility of subjects will be determined by the following inclusion and exclusion criteria. Subjects should meet all the inclusion criteria and none of the exclusion criteria.

5.1 PARTICIPANT INCLUSION CRITERIA

In order to be eligible for the study, subjects must fulfill all of the following criteria:

1. Males and females between 40 and 80 years of age, inclusive, in general good health
2. Ambulatory
3. Diagnosis of femorotibial OA in the target knee by standard American College of Rheumatology (ACR) criteria at Screening Visit 1 (clinical AND radiographic criteria); OA of the knee is not to be secondary to any rheumatologic conditions (e.g., rheumatoid arthritis)
4. Pain compatible with OA of the knee(s) for at least 26 weeks prior to Screening Visit 1
5. Primary source of pain throughout the body is due to OA in the target knee
6. Daily OA knee pain diary average NRS intensity score ≥ 4 and ≤ 8 in the target knee on the 11-point (0-10) NRS scale for the 7 days immediately preceding Day 1
7. Pain NRS scores recorded for the target knee on at least 4 out of the 7 days immediately preceding Day 1
8. Daily OA knee pain diary average NRS intensity score < 4 in the non-target knee on the 11-point (0-10) NRS scale for the 7 days immediately preceding Day 1
9. Pain NRS scores recorded for the non-target knee on at least 4 out of the 7 days immediately preceding Day 1
10. Total WOMAC score of 96-192 (out of 240) for the target knee at baseline regardless of if the subject is on symptomatic oral treatment (baseline questionnaire completed during the screening period prior to randomization)
11. Willingness to use an electronic diary on a daily basis in the evening for the screening period and 24-week study duration
12. Negative drug test for opioids and drugs of abuse, except alcohol and marijuana, at Screening Visit 1
13. Subjects with depression or anxiety must be clinically stable for 12 weeks prior to Screening Visit 1 and, if on treatment for depression or anxiety, be on 12 weeks of stable therapy
14. Full understanding of the requirements of the study and willingness to comply with all study visits and assessments
15. Subjects must have read and understood the informed consent form, and must have signed it prior to any study-related procedure being performed
16. Subject's Screening Visit 1 visit must occur while enrollment into the randomization cohort for which they are eligible is open

5.2 PARTICIPANT EXCLUSION CRITERIA

Any potential subject who meets one or more of the following criteria will not be included in this

study:

1. Women who are pregnant, lactating, or have a positive pregnancy result at Screening Visit 1
2. Women of child bearing potential who are sexually active and are not willing to use a highly effective method of birth control during the study period that includes double barrier, IUD, hormonal contraceptive combined with single barrier, or abstinence
3. Males who are sexually active and have a partner who is capable of becoming pregnant, neither of whom have had surgery to become sterilized or whom are not using a highly effective method of birth control
4. Body mass index (BMI) > 35
5. Partial or complete joint replacement in either knee
6. Currently requires:
 - a. regular use of ambulatory assistive devices (e.g., wheelchair, parallel bars, walker, canes, or crutches), or
 - b. use of a lower extremity prosthesis, and/or a structural knee brace (i.e., a knee brace that contains hardware)
7. Radiographic disease Stage 0, 1, or 4 in the target knee at Screening Visit 1 according to the Kellgren-Lawrence grading of knee OA as assessed by independent central readers
8. Previous participation in a Samumed clinical trial investigating SM04690
9. Any surgery (e.g., arthroscopy) in either knee within 26 weeks prior to Screening Visit 1
10. Any planned surgery during the study period. Non-surgical invasive procedures conducted for a diagnostic or therapeutic purpose scheduled during the study period are not prohibited (refer to [Section 7.6](#)).
11. Significant and clinically evident misalignment of either knee that would impact subject function, as determined by the Investigator
12. History of malignancy within the last 5 years; however, subjects with prior history of in situ cancer or basal or squamous cell skin cancer are eligible if completely excised. Subjects with other malignancies are eligible if they have been continuously disease free for at least 5 years prior to any study injection
13. Clinically significant abnormal screening hematology values, blood chemistry values, or urinalysis values as determined by the Investigator
14. Any condition, including laboratory findings (not included in the Screening Visit 1 laboratory tests) and findings in the medical history or in the pre-study assessments, that, in the opinion of the Investigator, constitutes a risk or contraindication for participation in the study or that could interfere with the study objectives, conduct, or evaluation
15. Comorbid conditions that could affect study endpoint assessments of the target knee, including, but not limited to, rheumatoid arthritis, psoriatic arthritis, systemic lupus erythematosus, gout or pseudogout, and fibromyalgia
16. Other conditions that, in the opinion of the Investigator, could affect study endpoint assessments of either knee, including, but not limited to, peripheral neuropathy (e.g., diabetic neuropathy), symptomatic hip osteoarthritis, symptomatic degenerative disc disease, and patellofemoral syndrome

17. Any diagnosed psychiatric condition that includes, but is not limited to, a history of mania, bipolar disorder, psychotic disorder, schizophrenia, schizoaffective disorder, major depressive disorder, or generalized anxiety disorder
18. Participation in a clinical research trial that included the receipt of an investigational product or any experimental therapeutic procedure, or an observational research trial related to osteoarthritis within 8 weeks prior to any study injection, or planned participation in any such trial; the last date of participation in the trial, not the last date of receipt of investigational product, must be at least 8 weeks prior to Screening Visit 1
19. Treatment of the target knee with intra-articular glucocorticoids (e.g., methylprednisolone) within 12 weeks prior to Screening Visit 1
20. Any intra-articular injection into the target knee with a therapeutic aim including, but not limited to, viscosupplementation (e.g., hyaluronic acid), PRP, and stem cell therapies within 24 weeks prior to Screening Visit 1; treatment of the target knee with intra-articular glucocorticoids greater than 12 weeks prior to Screening Visit 1 is allowed
21. Treatment with systemic glucocorticoids greater than 10 mg prednisone or the equivalent per day within 4 weeks prior to Screening Visit 1
22. Effusion of the target knee clinically requiring aspiration within 12 weeks prior to Screening Visit 1
23. Use of electrotherapy, acupuncture, and/or chiropractic treatments for knee OA within 4 weeks prior to Screening Visit 1 (refer to [Appendix 2](#))
24. Any known active infections, including urinary tract infection, upper respiratory tract infection, sinusitis, suspicion of intra-articular infection, hepatitis B or hepatitis C infection, and/or infections that may compromise the immune system such as human immunodeficiency virus (HIV) at Day 1
25. Use of centrally acting analgesics (e.g., duloxetine) (refer to [Appendix 2](#)) within 12 weeks prior to Screening Visit 1
26. Use of anticonvulsants not listed in [Appendix 2](#) within 12 weeks prior to Screening Visit 1, unless used for seizure or migraine prophylaxis
27. Subjects requiring the usage of opioids >1x per week within 12 weeks prior to Screening Visit 1
28. Topical local anesthetic agents (gels, creams, or patches such as the Lidoderm patch) used for the treatment of knee OA within 7 days of Screening Visit 1
29. Any chronic condition that has not been well controlled or subjects with a chronic condition who have not maintained a stable therapeutic regimen of a prescription therapy in the opinion of the investigator. In addition, subjects with a baseline HbA1c >9 will be excluded.
30. If on NSAIDs for the treatment of OA pain, subjects who have not maintained a stable regimen in the opinion of the Investigator at Screening Visit 1
31. Subjects who have a current or pending disability claim, workers' compensation, or litigation(s) that may compromise response to treatment
32. Subjects who are immediate family members (spouse, parent, child, or sibling; biological or legally adopted) of personnel directly affiliated with the study at any investigative site, or are directly affiliated with the study at any investigative site

33. Subjects employed by Samumed, LLC, or any of its affiliates or development partners (that is, an employee, temporary contract worker, or designee) responsible for the conduct of the study, or who are immediate family members (spouse, parent, child, or sibling; biological or legally adopted) of said employees responsible for the conduct of the study

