Detailed instructions for obtaining and managing the radiographs will be provided to the investigational center prior to the initiation of subject enrollment. The intent (as described in the Image Review Charter – Image Acquisition Guidelines) is that radiographs should be obtained in the posterior-anterior (PA) view, whenever possible.

All radiographs will be submitted to an independent radiologist who will document disease stage according to the Kellgren-Lawrence grading scale for compliance with inclusion/exclusion criteria, as well as JSW for efficacy assessments.

Widespread Pain Index and Symptom Severity (WPI&SS) Form

The WPI&SS assessment consists of a body map that determines a subject's areas of pain or tenderness [Widespread Pain Index (WPI)] and symptom severity (SS) questions ([Clauw 2014](#)). A WPI&SS assessment will be completed by the subject at Screening Visit 1 on paper.

Upon completion of the WPI&SS assessment, the subject will sign/initial and date the source document to indicate that the assessments are reported accurately.

The WPI&SS assessment sheets will be provided by the Sponsor and may not be reproduced.

Electronic Diary Device Provision and Training

Electronic diary device provision will occur at Screening Visit 2. Subjects will be trained on electronic diary and questionnaire completion at Screening Visit 2. Subject training will include details on what medications are NSAIDs. Detailed instructions for subject training and electronic questionnaire completion will be provided to the investigational center. Electronic devices are to be returned to the site at Week 24 (EOS)/ET.

Electronic devices will store completed questionnaire data for up to 30 days. Therefore, it is recommended that site personnel review study subject ePRO data and compliance reports in the ePRO vendor web portal (StudyWorks) at least once a week or more frequently as needed to ensure timely subject completion and transmission of questionnaire data between study visits.

Pain Numeric Rating Scale (NRS)

The pain NRS is an 11-point scale (0-10) for subject self-reporting of average knee pain in the last 24 hours. A pain NRS for each knee will be completed daily by the subject during the screening period from Screening Visit 2 until Day 1 to assess subject ability to be compliant with a daily pain assessment. During the screening period, daily pain NRS assessments will be

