4. STUDY ENDPOINTS

4.1. Primary Endpoints

The primary endpoints of this study include:

1. Evaluate change from baseline OA pain in the target knee as assessed by the weekly averages of daily pain Numeric Rating Scale (Pain NRS) at Week 24
2. Evaluate change from baseline OA pain in the target knee as assessed by Western Ontario and McMaster Universities Osteoarthritis Index (WOMAC) Pain subscore at Week 24
3. Evaluate change from baseline OA function in the target knee as assessed by WOMAC Physical Function (WOMAC Function) subscore at Week 24
4. Evaluate change from baseline in medial joint space width (mJSW) as documented by radiograph of the target knee at Week 24

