7.2. ANCOVA Model for Continuous Efficacy Outcomes

ANCOVA models will be used for all continuous efficacy outcome measures summarized by change from baseline in order to test the following four hypotheses:

$$H_0: (\beta_i - \beta_0) = 0$$

$$H_A: (\beta_i - \beta_0) \neq 0, \text{ where } i = 1,2,3,4$$

In the statement above, β is the least squares estimate in the change in the continuous efficacy outcome from baseline at each timepoint (where β_0 is the estimate for vehicle), and i represents each of the four SM04690 treatment groups.

Least squares estimate of difference between each treatment group and placebo in the change in the continuous efficacy outcome from baseline at each timepoint, adjusted for baseline value, will be reported along with unadjusted 95% confidence intervals and P values.

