7.3. Analysis of Primary Efficacy Endpoints

The change from baseline in weekly Pain NRS, WOMAC Pain, WOMAC Function and mJSW at Week 24 will be analyzed with the ANCOVA model described in Section 7.2. Figures displaying the change in outcome over time will be provided for the FAS and mFAS.

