10.2. Demographic and Baseline Characteristics

Demographic and baseline characteristics, including gender, race, ethnicity, age, weight, height, body mass index (BMI), Kellgren-Lawrence (KL) grade, OA laterality, WPI and SSQ2 will be presented by treatment group. Continuous variables will be summarized with descriptive statistics and categorical variables will be summarized with frequencies and percentages. The summaries will be provided for each analysis set and OA phenotype. Subject level listings will also be provided.

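### Kellgren-Lawrence grade is read centrally and tabulated by arm but is not a covariate in the mJSW ANCOVA; pre-specifying it is a minor, nearly free improvement

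*Protocol*

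**What the plan says.** **Entry and reading.** Protocol 5.2, criterion 7, excludes "Radiographic disease Stage 0, 1, or 4 in the target knee at Screening Visit 1 according to the Kellgren-Lawrence grading of knee OA", as judged by independent central readers. Protocol 7.1.1 adds: "All radiographs will be submitted to an independent radiologist who will document disease stage according to the Kellgren-Lawrence grading scale". Eligible target knees are therefore grade 2 or 3, and the grade is on file before randomisation.

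**Endpoint.** The fourth primary endpoint in SAP 4.1 is "Evaluate change from baseline in medial joint space width (mJSW) as documented by radiograph of the target knee at Week 24". Films are taken at Screening Visit 1 and Week 24 only (SAP 5.2.9).

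**Model.** SAP 7.3: "The change from baseline in weekly Pain NRS, WOMAC Pain, WOMAC Function and mJSW at Week 24 will be analyzed with the ANCOVA model" of SAP 7.2. That section reports dose-vehicle differences "adjusted for baseline value, will be reported along with unadjusted 95% confidence intervals and P values". Protocol 10.4.2 also names the baseline value as the only adjustment.

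**Other uses of the grade.** Randomisation is stratified by laterality and WPI&SS, not by grade (Protocol 10.6.1; SAP 3.2). Grade is not among the subgroups of SAP 7.5.5. In the SAP it appears only in the baseline table: "Kellgren-Lawrence (KL) grade, OA laterality, WPI and SSQ2 will be presented by treatment group" (SAP 10.2), for each analysis set and phenotype.

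**Sensitivity analyses.** The LOCF and MMRM analyses in SAP 9.4 cover Pain NRS, WOMAC Pain, WOMAC Function and Patient Global Assessment, not mJSW. The mJSW ANCOVA is repeated across analysis sets and phenotypes (SAP 7.1, 7.5.5), always with the same covariate.

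**The concern.** mJSW is the only structural primary endpoint, and it has a single post-baseline film. Its Week 24 ANCOVA estimates go into the MCP-Mod dose-response step (SAP 7.6), which serves the primary objective. All four doses are compared with the same vehicle arm, so a chance excess of grade 3 knees in vehicle would move all four contrasts in the same direction.

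Baseline mJSW may not capture everything that grade says about later change. If grade predicts 24-week change beyond baseline mJSW, the planned model leaves that part in the residual and in any realised imbalance. The baseline table will show the imbalance, but no planned mJSW analysis responds to it. The sponsor would then have to leave the question open or add grade after seeing the table, and the second course could be criticised as data-driven.

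**Working it through.** **Inputs from the documents.** About 630 subjects in six equal arms (Protocol 10.5): 630/6 = 105 per arm. The cohort with unilateral OA and no widespread pain is capped at 240 (Protocol 7.3.2): 240/6 = 40 per arm. It is one of the three main analysis populations in SAP 7.1. The plan gives no power, SD or effect size, so it has no figure of its own to reproduce.

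**Assumptions (none is in the documents).** Share of grade 3, p = 0.5 (0.3 to 0.6 where shown). Grades 2 and 3 differ in baseline mJSW by s = 0.5 to 1.5 within-grade SD. Grade effect on change beyond baseline mJSW, g = 0, 0.2 or 0.5 residual SD.

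**Step 1: chance imbalance between two arms.** SD = sqrt(2p(1-p)/n), with p = 0.5:
- n = 105: sqrt(0.5/105) = 0.069; 95% range 1.96 x 0.069 = +/-13.5 percentage points.
- n = 40: sqrt(0.5/40) = 0.112; 95% range +/-21.9 points.

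Over p = 0.3 to 0.6 the ranges are +/-12.4 to 13.5 and +/-20 to 22 points. At p = 0.5 a single dose-vehicle pair differs by more than 10 points with probability 15% (n = 105) or 31% (n = 40, from binomial counts). At least one of the four doses differs from vehicle by more than 10 points with probability 32-40% (n = 105) or 64-71% (n = 40) over p = 0.3 to 0.6.

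**Step 2: what baseline mJSW leaves.** Only the part of the imbalance that baseline mJSW does not explain can shift the contrast. At p = 0.5 that fraction is 1/(1 + s²/4): 0.94, 0.80 and 0.64 for s = 0.5, 1.0 and 1.5. Expected shift = g x imbalance x fraction.

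| n per arm | imbalance | g = 0.2 | g = 0.5 |
|---|---|---|---|
| 105 | 0.135 | 0.017-0.025 SD | 0.043-0.064 SD |
| 40 | 0.219 | 0.028-0.041 SD | 0.070-0.103 SD |

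Simulation of one dose against vehicle (4,000 runs per setting) agrees within its noise: 0.01-0.02 and 0.04-0.06 SD at n = 105, and 0.03-0.04 and 0.07-0.11 SD at n = 40. In standard errors these are 0.10-0.17 (g = 0.2) and 0.31-0.40 (g = 0.5) at n = 105, and 0.31-0.47 for g = 0.5 at n = 40. With g = 0 the planned model removes the effect of the imbalance.

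**Step 3: precision.** Residual variance without grade is 1 + g² x 0.25 x fraction. For g = 0.5 and s = 0.5 it is 1 + 0.25 x 0.25 x 0.94 = 1.059, an SE ratio of 1/sqrt(1.059) = 0.972 before the lost degree of freedom. Simulated ratios (SE with grade over SE without) run from 0.974 to 1.002 at n = 105 and from 0.978 to 1.007 at n = 40.

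**Step 4: error rates.** Simulated two-sided type I error at n = 105 is 4.4-5.4% without grade and 4.6-5.7% with it. At n = 40 it is 4.7-5.9% and 4.7-6.1%. The Monte Carlo SE is about 0.3 points.

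Power for a 0.4 SD effect at n = 105 with s = 1.0:

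| g | without grade | with grade | change (points) |
|---|---|---|---|
| 0 | 82.5% | 82.2% | -0.3 |
| 0.2 | 81.1% | 81.2% | +0.1 |
| 0.5 | 80.1% | 82.0% | +1.9 |

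**The case against.** The strongest reply is that ANCOVA on the endpoint's own baseline is a valid pre-specified analysis. Baseline mJSW is a continuous measure of the same compartment of the same knee, entry is already confined to two adjacent grades, and the confidence interval allows for chance imbalance. All of that stands.

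It also rules out stronger readings that a reader might infer:
- **That stage imbalance goes uncorrected.** The part carried by joint space is corrected.
- **That the contrasts are biased or type I error is inflated.** Type I error stays near 5% in either model (Step 4).
- **That the exclusion criterion shows grade 2 versus 3 to be prognostic.** It is an eligibility rule, and no passage reports an effect of grade on 24-week change.
- **That the shift is the raw imbalance times the grade effect.** This gives 0.135 x 0.2 to 0.5 = 0.03-0.07 SD at 105 per arm and overstates it, because the model acts on the imbalance left after baseline mJSW.

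Two further objections carry some weight. The stratification factors, laterality and WPI&SS, are also absent from the model, and that is the more usual complaint; but it is a separate point and does not answer this one. Protocol 10.4.2 names the adjustment, so the cost may not be purely an SAP edit. Against that, Protocol 10.1 leaves the full description of the analyses to the SAP.

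**Conclusion.** The point holds as a minor free improvement, not as an error in the plan. Grade is known for each target knee before randomisation, yet no planned mJSW analysis uses it.

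The possible gain is modest. At the 95% limit of imbalance the shift stays below half a standard error, even at the largest assumed effect. The standard error changes by between -2.6% and +0.2% at 105 per arm. In the 40-per-arm population a weak effect (g = 0.2) would not repay the lost degree of freedom, but that loss is under 1% of the standard error. Nothing here shows that a dose decision would change.

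All sizes rest on the assumed share of grade 3, separation in baseline mJSW and residual grade effect. If grade adds nothing beyond baseline mJSW, there is nothing to gain. The better reason to act is that the baseline table will display any imbalance, and the response to it is best fixed in advance.

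**What to change.** Before database lock, add baseline grade (2 vs 3, central read of the Screening Visit 1 film) as a fixed covariate beside baseline mJSW in the mJSW ANCOVA, for the dose-vehicle contrasts (SAP 7.3) and for vehicle versus sham (SAP 7.5.4). Use those estimates as the mJSW input to MCP-Mod (SAP 7.6). Align the wording of Protocol 10.4.2 if the sponsor considers that the SAP alone cannot add a covariate.

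At minimum, keep the planned model and pre-specify the grade-adjusted one as an mJSW sensitivity analysis in SAP 9.4, where mJSW has none.

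State which read supplies the covariate, since Protocol 5.2 refers to central readers and 7.1.1 to one radiologist, and how a knee enrolled outside grades 2 and 3 is coded. If the database is already locked, label the analysis post hoc.

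Cost: one model term and one degree of freedom. No new visit, film or reading is needed.

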5.3 LIFESTYLE GUIDELINES

5.3.1 CONTRACEPTION

From Screening Visit 1 until Week 24 (EOS)/ET, all subjects must agree to be strictly abstinent from sexual intercourse or use an acceptable form of contraception as defined by this protocol if the subject or their partner is capable of becoming pregnant.

Sexually active subjects must use one of the following methods of contraception from Screening Visit 1 until Week 24 (EOS)/ET:

1. Use of a condom for males with a vasectomy (vasectomy must have been performed at least 6 months prior to Screening Visit 1)
2. Males without a vasectomy or a vasectomy performed within 6 months prior to Screening Visit 1 must use a condom and be instructed that their female partner(s), if any, must be of nonchildbearing potential or use another form of highly effective birth control which includes the following:
 - a. Double barrier methods of contraception such as condom plus diaphragm or cervical/vault cap with spermicide (i.e., physical plus chemical)
 - b. Established hormonal contraceptive methods. Females who are using hormonal contraceptives must have had consistent use of the same hormonal contraceptive product for at least 4 weeks prior to dosing and must continue to use the same contraceptive during the study
 - c. Intrauterine device (IUD)
 - d. Surgically sterile (e.g., bilateral tubal ligation/occlusion, hysterectomy)
 - e. Postmenopausal
3. Women of childbearing potential must agree to use a highly effective method of contraception (as described in #2 above) and be instructed that their male partner(s), if any, must use a condom

